Strategies for evaluating an intervention's mechanisms of behavior change are comparatively well established^{55, 64-67}. Morgenstern and Longabaugh's⁶⁸ causal chain to demonstrate skill acquisition as a mechanism of CBT proposed four criteria, which included evidence that inclusion of coping behaviors as a covariate reduced the effect of CBT on drinking outcome (statistical mediation⁶⁹). **However, much of the evidence regarding skills acquisition from CBT trials for alcohol use fails to meet all four of these criteria**^{16, 68, 70, 71}. Several methodological features likely contribute to the mixed evidence regarding CBT's mechanisms: First, most trials evaluating clinician-delivered interventions face issues of variability in treatment delivery that may confound the evaluation of mechanisms. This includes variability in fidelity to the intervention⁷²⁻⁷⁴, dose and quality of delivery⁷⁵, as well as '*therapist effects*' that may directly affect the active treatment ingredients hypothesized to be responsible for contributing to behavior change. Clinicians delivering standardized treatment in clinical trials regularly show substantial differences in the outcomes of clients they treat⁷⁶⁻⁷⁸, and in some trials, '*therapist effects*' account for more variability in outcome than treatment factors⁷⁹⁻⁸¹. Furthermore, distinguishing non-specific factors from specific active ingredients has proven difficult in trials examining mediators across clinician-delivered treatments^{58, 82, 83}. **Specific effects are inseparable from 'relational' effects (e.g., therapeutic alliance) when treatments are delivered in the context of an interpersonal relationship**⁷⁶. Second, there are relatively few reliable measures of skills acquisition and implementation^{16, 59, 68}, as many self-reported assessments may not be adequately sensitive to the specific skills taught nor measured at the appropriate intervals to demonstrate change prior to the outcome^{55, 65}. Third, given the complexity of behavior change, trials have been limited by inclusion of only one level of analysis of the mechanism, rather than considering the contributions of multiple processes to form a more complete understanding of how, and for whom, CBT works. For instance, there is considerable evidence that chronic, heavy alcohol use affects cognitive abilities associated with controlled and effortful processing of novel information, including executive functions and fluid cognitive abilities⁸⁴⁻⁸⁹, which have been shown to affect treatment processes⁹⁰⁻⁹³, and may affect the delivery of a cognitively-demanding therapy such as CBT (e.g., moderation of a mediator). Lastly, traditional methods for demonstrating statistical mediation (e.g., causal steps approach) have been limited by testing single mechanisms with inadequate power for detecting mediated effects^{94, 95}. More advanced statistical approaches have indicated the improvement in coping skills may mediate the effect of CBT on reductions in primary drug use⁹⁶, marijuana⁹⁷, gambling⁹⁸, and chronic pain⁹⁹.

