3. Treatment phase: Study treatments will last 8 weeks. During the treatment phase, all participants will meet weekly virtually either via Zoom and/or phone with research staff for completion of self-report and interview assessments. In all conditions, we will closely monitor participant treatment response and safety via BAC, urine screens which are taken by the clinic on the clinic's usual schedule and assessment of psychiatric status. Although in our experience this is a very rare event in behavioral trials¹⁷⁷, including those of computer-delivered interventions^{110, 119, 122}, participants who show significant deterioration (e.g., significant increases in alcohol use or psychiatric symptoms that cannot be managed within the protocol) will be regarded as symptomatic failures, withdrawn from the treatment arm of the study, and referred for

appropriate treatment (typically a more intensive level of care). See Protection of Human Subjects, below.

4. Termination, post-treatment assessment, and follow-up: At the end of the 8-week treatment period, all participants will be re-interviewed (see Assessments) virtually either via Zoom and/or phone. Access to the CBT4CBT program will be terminated, and *participants in all three conditions will be offered the opportunity to continue in treatment as usual at MCCA or SATU if desired/needed*. Follow-up interviews (using the full post-treatment battery that includes treatment utilization) will be conducted 1, 3, and 6 months after termination virtually either via Zoom and/or phone. We will attempt to follow all participants in our intention-to-treat sample, using strategies that have been successful in our multiple previous studies¹⁷⁸, where our *current rate of follow-up approaches 90-95% across studies*^{149, 179, 180}.

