Latent growth curve modeling will be the principal strategy for evaluating mediation using Mplus version 7²⁵¹. The product of coefficients method^{18, 19} will be

used to determine the mediating effects of skills acquisition during the treatment period *on PDA* during follow-up. In this model (Figure 4), M_1 through M_3 are repeated measures (weeks 0, 4, 8) of the mediator ‘acquisition of skills’ (as measured by ARRT¹⁵, CSI¹⁶, homework completion and quality, and knowledge assessment⁵⁰). Both the intercept (I_M) and slope (S_M) act as joint mediators of the effect of X (treatment condition) on Y (PDA during 6 month follow-up), allowing the examination of the average level (i.e., intercept) and average change over time (i.e., slope) of the mediator. We will be using the 6-month period following treatment as our alcohol use outcome in this model to support the temporal relation criterion⁶⁴, as well as to evaluate the delayed emergence of CBT’s effect on alcohol use¹³⁹. This model will test:

- **H2a:** Effect of CBT on acquisition of skills (a_2 path: $X \rightarrow M$): Clinician-CBT>TAU; CBT4CBT>TAU
- **H2b:** Effect of change in acquisition of skills on PDA by month during follow-up (b_2 path: $M \rightarrow Y$)
- **H2c:** Indirect effect of CBT on PDA via change in acquisition of skills ($a_2 * b_2 / se_{a2} * se_{b2}$)

Adequacy of sample size: Parameter estimates from our initial trial of CBT4CBT that supported coping skills acquisition as a mediator of treatment effects on substance use⁹⁶ were used to estimate effect sizes of treatment condition on PDA via skills acquisition ($a=.26$; $b=.59$). Based on these effect sizes and power estimates for testing mediation derived from a simulation study⁹⁴, we will have adequate power (.80) to detect significant mediating effects with the proposed sample size of 60 per condition.

Exploratory Aims:

[figure not shown]

(a) Pre-treatment cognitive function as indicated by measures from CANTAB tasks (sustained attention,

working memory, response inhibition, cognitive flexibility, planning, decision-making) will be evaluated as moderators of CBT's effect on PDA (clinician-delivered CBT and CBT4CBT vs. TAU), using linear moderation regression models, such that a significant interaction between pre-treatment cognitive function measures and treatment condition would indicate a moderated effect (i.e., the effect of CBT on PDA is dependent on levels of pre-treatment cognitive function);

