The procedures for SAE reporting include written documentation using the clinical notes related to the adverse event and specific forms detailing the event with a sign-off by all appropriate supervisory personnel. Communication of recommendations and decisions from all parties (DSMB, Yale Human Investigations Committee, and MCCA or SATU Administration) are made back to the investigator in a timely manner. We will report all protocol amendments or changes in the informed consent form to NIAAA as well as any temporary or permanent suspension of patient accrual.

- d. For multi-site studies for which the Yale PI serves as the lead investigator: **N/A**
 - i. How will adverse events and unanticipated problems involving risks to subjects or others be reported, reviewed and managed?
 - ii. What provisions are in place for management of interim results?

iii. What will the multi-site process be for protocol modifications?

11. Statistical Considerations: Describe the statistical analyses that support the study design.

Aim 1 - Evaluation of treatment effects:

The principal strategy for assessing the efficacy of the study treatments on outcome will be random effects regression models for continuously measured primary (e.g., percentage of days abstinent - PDA) and secondary (e.g., percentage of heavy drinking days, quality of life, etc.) outcomes. Our research group has used these methods to evaluate main and interaction effects, with appropriate covariates (e.g., retention, compliance with treatment) in multiple previous trials^{121, 138, 142, 171, 172}. We will include treatment utilization data during the follow-up period as a covariate in analyses evaluating treatment effects through follow-up.

Analysis of treatment effects at post-treatment and follow-up will include the following contrasts:

- **H1a:** *Main effect for CBT on PDA by month during treatment:* Clinician-CBT and CBT4CBT>TAU.
- **H1b:** *Main effect for CBT on PDA by month through follow-up:* Clinician-CBT and CBT4CBT>TAU.

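### Aim 2 rests temporal order on taking PDA after treatment, but its described model omits treatment-period PDA, so skill scores that partly follow reduced drinking could appear as a mediating path

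*Combined protocol and SAP*

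**What the plan says.** Section C.2.f, Aim 2, specifies a latent growth curve model tested by the product of coefficients. The skills measures "are repeated measures (weeks 0, 4, 8) of the mediator". Their intercept and slope "act as joint mediators of the effect of X (treatment condition) on Y (PDA during 6 month follow-up"). H2b is the "Effect of change in acquisition of skills on PDA by month during follow-up", and H2c is the indirect effect through that path. The only device offered for temporal order is the placing of the outcome: "We will be using the 6-month period following treatment as our alcohol use outcome in this model to support the temporal relation criterion". The same sentence gives delayed emergence of CBT's effect as a second purpose. Section V, item 11 repeats the hypotheses and this rationale.

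Neither place names baseline PDA, treatment-period PDA, a drinking growth process or a reverse path. The covariates in C.2.f (retention, compliance, treatment utilization during follow-up) belong to Aim 1. The exploratory models add cognition, alliance, self-efficacy, motivation, AUDIT and Shipley scores, but not drinking during treatment.

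H1a meanwhile tests a "Main effect for CBT on PDA by month during treatment". In the pilot (C.1.e), PDA rose more in the CBT4CBT arms than in treatment as usual over the 8 weeks, and change-strategy scores in the CBT4CBT arms rose from 31.9 to 46.1 over the same period.

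**The concern.** Placing the outcome after the mediator gives temporal order only if the outcome has not already begun to move. Here both variables are expected to move during treatment. If drinking falls first and skill scores follow, and treatment-period drinking persists into follow-up, skill slope will correlate with follow-up PDA without affecting it. The described model has nothing to tell this apart from skills rising first.

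The route is most plausible for the Coping Strategies Inventory, a self-report of how often alcohol-avoidance strategies are used. It is less so for the role-play test (ARRT) or the knowledge quiz.

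Aim 2 is a specific aim whose conclusion concerns mechanism. Section A2 lists, among the weaknesses of earlier self-report skills measures, that they were "nor measured at the appropriate intervals to demonstrate change prior to the outcome". Adjusting for baseline PDA would not settle the matter, because this path arises after randomisation.

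**Working it through.** **The plan's own figure.** C.2.f states power of .80 for mediation with a = .26, b = .59 and 60 per condition. Two regressions (M on X; Y on X and M), with X standardised, unit residual SDs, no direct effect, 60 v 60 and a two-sided .05 test of both paths, give .804. The figure reproduces, but it presupposes that the skills-to-PDA path is causal.

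**Inputs from the documents.** 60 per arm, ICC .6 for monthly PDA, PDA effect during treatment d = .35, alpha .05 (all C.2.f; Aim 1 inputs apart from the sample size; two-sided assumed).

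**Assumed, not in the documents.** Within-arm correlation ρ of skill slope with drinking, .2 to .4. Correlation r_b of baseline with later PDA, .6 or .4. Direct CBT effect on skill slope δ = 0 or .5. Skills have no effect on drinking.

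**Set-up.** Monthly PDA has unit SD and pairwise correlation .6 after baseline. T is the mean of treatment months 1 and 2, and Y is the mean of six follow-up months.

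- Var(T) = .6 + .4/2 = .80
- Var(Y) = .6 + .4/6 = .667
- corr(T, Y) = .6/√(.80 × .667) = .82

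**b path, slope follows the level of T.** The spurious within-arm correlation of slope with Y is .82ρ = .16, .25, .33. With n = 120 and 117 df, t ≈ r√117/√(1 − r²) = 1.80, 2.75, 3.76. Against a critical value of 1.98, the rejection rates are about 43%, 78% and 96%. Simulation gives 42%, 78% and 96%.

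**b path, slope follows change from baseline, T − P0.** Cov(T − P0, Y) = .6 − r_b. At r_b = .6 this is zero, so the test stays near 5%. At r_b = .4, Var(T − P0) = .80 + 1 − .80 = 1.0, and the correlation with Y is .2/√.667 = .245. Multiplied by ρ, this is .05 to .10.

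| Slope follows | Model for follow-up PDA | b path falsely significant |
|---|---|---|
| Level | As described | 42–96% |
| Level | Plus baseline PDA | 19–59% (r_b = .6); 31–88% (r_b = .4) |
| Change | As described | 4–5% (r_b = .6); 8–19% (r_b = .4) |
| Change | Plus baseline PDA | 21–79% |
| Either | Plus baseline, month-1 and month-2 PDA | about 5% |

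**Full mediation (both paths significant), level tracking, model as described.** The arm difference in slope is ρ × .35/√.80 + δ, with standard error √(2/60) = .183.

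- δ = 0 (skill gains come only from reduced drinking): differences of .078 to .157, so the a path is significant in about 7–13% of trials. Multiplied by the b-path rates, this gives about 3–13%. If both paths were truly null the rate would be about .05 × .05 = .25%.
- δ = .5 (CBT also teaches inert skills): differences of .578 to .657, so the a path is significant in about 88–95%. Mediation is falsely found in about 38–92%.

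**Candidate remedies at 60 v 60.**

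- A lagged model (week-4 skills to weeks 5–8 PDA, given weeks 1–4 PDA and week-0 skills) holds about 5% under the null. Its power is 62–64% for a true lagged effect of .2 and 93–94% for .3. The same lag without earlier PDA rejects falsely in 56–91%.
- Conditioning on all treatment-period PDA cuts power for the indirect effect from .60 to .21, or from .78 to .35, when skills truly work by cutting drinking within treatment.

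**The case against.** Several stronger readings are tempting, and the documents do not support them.

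- *A reader might infer that skill gains which only follow reduced drinking would pass as mediation.* In that scenario the a path is weak, and the unadjusted test passes in about 3–13% of trials. The high rates need CBT also to teach skills directly. That is H2a, so the scenario is reasonable, but it is not pure reverse causation.
- *That 42–96% is the plan's error rate.* It holds only if slope follows the level of drinking. Under change tracking the unadjusted rate is 4–19%. The documents do not say which applies, and ρ is assumed.
- *That ICC .6 shows the outcome has mostly moved by week 8.* An ICC describes stable differences between people, which may predate treatment. C.2.c, item 5 expects further gains after treatment.
- *That delayed emergence cannot be isolated.* H2b refers to PDA by month, which might separate later change. The text does not settle this, and the path diagram is not shown.
- *That the plan repeats the fault it criticises.* It answers that fault in part, with a role-play test and three skills measurements before follow-up. It says only that timing supports the criterion.

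The calculations also use an observed slope, mean follow-up PDA and joint significance, without the mediator intercept. The plan uses a latent model with the product of coefficients, so the rates are indicative.

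What stands is that nothing in the Aim 2 text lets the analysis examine direction, and that baseline adjustment alone does not supply this.

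**Conclusion.** The concern holds in a limited form. As described in the text, Aim 2 relies on outcome timing while mediator and outcome are expected to change together, so a spurious H2b path is possible and H2c could pass with it. The size depends mainly on two things the documents do not give: how strongly skill scores follow drinking, and whether they follow its level or its change. Over the assumed range the unadjusted H2b error runs from nominal to 96%. False mediation under level tracking runs from about 3% to 92%, and the upper part of that range requires CBT to teach skills that do nothing. All of it requires treatment-period drinking to persist into follow-up. The data needed to examine direction are already collected, so this should be corrected; it does not invalidate the planned model.

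**What to change.** Keep the planned model and prespecify one sensitivity model beside it. Section C.2.c, item 3 says "all participants will meet weekly virtually either via Zoom and/or phone with research staff for completion of self-report and interview assessments", and the Schedule of Assessments marks TLFB weekly, so no new data are needed. Use a lagged or parallel-process model: for example, week-4 skills predicting weeks 5–8 PDA, given weeks 1–4 PDA, baseline PDA and week-0 skills. Test the reverse path, from early PDA to later skills, in the same model. A parallel process that only lets the two slopes correlate is not enough, because it tests no direction.

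Report H2b and H2c from both models. Describe the planned model alone as showing association consistent with mediation, not as establishing temporal precedence or delayed emergence.

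Do not use a model that conditions on all treatment-period PDA as a pass/fail gate. If skills work by cutting drinking within the 8 weeks, it removes part of the true effect.

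The cost is a paragraph of SAP text and one more Mplus model. That model will have less power than the planned one, and the lagged example addresses direction within treatment rather than follow-up PDA itself.

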Adequacy of sample size: *H1a* – Using conventional effect size estimates, we determined that our proposed sample size of 60 per condition would be sufficient for detecting a small-medium effect ($d=.35$) of treatment on PDA using a random effects regression model (2 groups, PDA by month, 3 data points, ICC=.6, alpha=.05, beta=.80). *H1b* – The proposed sample is sufficient to detect a medium effect ($d=.50$) through the follow-up period with a random effect regression model (2 groups, PDA by month, 7 data points, ICC=.6, alpha=.05, beta=.80). These effect sizes are conservative, based on estimates from completed studies of CBT4CBT^{119, 122}.

Cost-effectiveness analyses: [name] of American University, an expert in cost analyses, particularly of behavioral therapies with substance using populations²⁴³⁻²⁵⁰, is a member of the Scientific Advisory Board as well as a consultant to [name] NIDA-

supported Psychotherapy Development Center. In this capacity, he directs cost-effectiveness evaluations of Center projects, including all those related to CBT4CBT as well as the proposed study. *He was involved in the design of the Program and Client Costs for Substance Abuse Treatment (PACC-SAT)*^{14, 166}, *the instrument that will be used to assess participants use of a wide variety of physical and mental health services, substance use and legal services utilization. The PACC-SAT covers the 12 months prior to randomization, the full-8 week treatment period, and the entire follow-up period* (See Schedule of Assessments). The general approach used to evaluate cost-effectiveness of the protocol interventions will be to evaluate the relationship between value of resources used in intervention implementation (e.g., *costs associated with the facility, staff, and transportation*) and nonmonetary outcomes produced by the intervention (e.g., *reduction in drinking behavior and drinking consequences, improvement in quality of life*). This will include calculating the total cost for each treatment condition, cost per participant in each condition, as well as outcomes of ‘alcohol-free days’, and comparing the average cost per ‘alcohol-free day’ gained per month across treatment conditions, *using strategies outlined in [name] previous work*^{243, 246, 247, 249, 250}.

Aim 2 – Evaluation of skills acquisition as mediator of CBT effects:

[figure not shown]

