Adequacy of sample size: *H1a* – Using conventional effect size estimates, we determined that our proposed sample size of 60 per condition would be sufficient for detecting a small-medium effect ($d=.35$) of treatment on PDA using a random effects regression model (2 groups, PDA by month, 3 data points, ICC=.6, alpha=.05, beta=.80). *H1b* – The proposed sample is sufficient to detect a medium effect ($d=.50$) through the follow-up period with a random effect regression model (2 groups, PDA by month, 7 data points, ICC=.6, alpha=.05, beta=.80). These effect sizes are conservative, based on estimates from completed studies of CBT4CBT^{119, 122}.

Power calculations	Power	Estimated effect size	# of datapoints	Sample size per cell
H1a: (Clinician CBT + CBT4CBT stand-alone) v TAU, main effect for active treatment	.80	.35	3	60
H1b : (Clinician CBT + CBT4CBT stand-alone) v TAU, main effect for follow up	.80	.50	7	60

Aim 2 – Evaluation of skills acquisition as mediator of CBT effects:

Latent growth curve modeling will be the principal strategy for evaluating mediation using Mplus version 7²⁵¹. The product of coefficients method^{18, 19} will be used to determine the mediating effects of skills acquisition during the treatment period on PDA during follow-up. We will be using the 6-month period following treatment as our alcohol use outcome in this model to support the temporal relation criterion⁶⁴, as well as to evaluate the delayed emergence of CBT's effect on alcohol use¹³⁹. This model will test:

- **H2a:** *Effect of CBT on acquisition of skills (a₂ path: X→M):* Clinician-CBT>TAU; CBT4CBT>TAU
- **H2b:** *Effect of change in acquisition of skills on PDA by month during follow-up (b₂ path: M→Y)*

- **H2c:** *Indirect effect of CBT on PDA via change in acquisition of skills ($a_2 * b_2 / se_{a2} * se_{b2}$)*

Adequacy of sample size: Parameter estimates from our initial trial of CBT4CBT that supported coping skills acquisition as a mediator of treatment effects on substance use⁹⁶ were used to estimate effect sizes of treatment condition on PDA via skills acquisition ($a=.26$; $b=.59$). Based on these effect sizes and power estimates for testing mediation derived from a simulation study⁹⁴, we will have adequate power (.80) to detect significant mediating effects with the proposed sample size of 60 per condition.

SECTION VI: RESEARCH INVOLVING DRUGS, BIOLOGICS, RADIOTRACERS, PLACEBOS AND DEVICES

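### The Aim 2 mediation model, as described in the text, omits baseline PDA, so pre-treatment drinking can bias the skills-to-drinking path (H2b) and, through it, the indirect effect (H2c)

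*Combined protocol and SAP*

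**What the plan says.** Section C.2.f, Aim 2, specifies a latent growth curve model. Skills are measured at weeks 0, 4 and 8 and summarised by a latent intercept and slope, which jointly mediate the effect of condition on PDA over the six-month follow-up. Section V, item 11 (Statistical Considerations) repeats the purpose: "to determine the mediating effects of skills acquisition during the treatment period on PDA during follow-up". H2b is worded as "Effect of change in acquisition of skills on PDA by month during follow-up". H2c is the product of the two path coefficients, with a statistic that divides by the product of their standard errors.

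The safeguard offered for the path from skills to drinking is timing: follow-up PDA is used "as our alcohol use outcome in this model to support the temporal relation criterion".

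Neither place names baseline PDA, or any other covariate, for Aim 2. The covariates listed in C.2.f (retention, compliance, treatment utilization during follow-up) belong to Aim 1 and do not include baseline PDA either. AUDIT severity appears only as an exploratory moderator. The Schedule of Assessments places the Timeline Follow-Back at screening/pre-treatment, so baseline PDA can be derived.

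**The concern.** Randomisation protects the effect of condition on skills (the a path). It does not protect the effect of skills on later drinking (the b path), because participants are not allocated to a level of skill change. If pre-treatment drinking influences how much skill a person gains and also how much that person drinks later, skill change and follow-up PDA will be associated even when skills do nothing.

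Measuring the outcome after the mediator rules out later drinking as a cause of earlier skill change. It does not rule out a cause that precedes both. Urn balancing on severity (C.2.c) and the baseline-equivalence check (C.2.f) concern balance between arms, so they too leave the b path open.

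H2b and H2c carry the trial's claim about mechanism, one of its two main aims. A b path that mixes the effect of skills with initial drinking would weaken that claim in either direction.

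**Working it through.** **Inputs from the documents.** There are 60 participants per condition: 120 for one CBT arm against TAU, 180 for all three arms. Mediation power assumes a = .26 and b = .59. Alpha is .05, stated for Aim 1 ("ICC=.6, alpha=.05, beta=.80"); Aim 2 gives no alpha, so two-sided .05 is assumed here.

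**Inputs assumed.** r1 is the correlation of baseline PDA with skill slope, from 0 to .3. r2 is the correlation of baseline PDA with follow-up PDA, .4 or .5. The documents give neither. No attrition is assumed.

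**The plan's own figure.** The plan says "we will have adequate power (.80) to detect significant mediating effects with the proposed sample size of 60 per condition". Simulating M = aX + e and Y = bM + e with unit residual SDs, and requiring both paths to be significant, gives .80 (continuous X) and .81 (X coded ±1) at n = 120. The stated power therefore reproduces under those codings; with X coded 0/1 it is .30. That calculation takes b as unconfounded, so it does not bear on the question below.

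**False-positive rate for b when the true b is zero.** With baseline PDA omitted, the spurious correlation is r = r1 × r2. The expected test statistic is d = atanh(r) × √(N − 3), and the rejection probability is Φ(d − 1.96) + Φ(−d − 1.96).

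Example for N = 180, r1 = .2, r2 = .4: r = .08; atanh(.08) = .0802; √177 = 13.30; d = 1.07; rejection 19%.

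| r1 | r2 | spurious r | N = 120 | N = 180 |
|---|---|---|---|---|
| 0 | .4 or .5 | 0 | 5% | 5% |
| .1 | .4 | .04 | 7% | 8% |
| .1 | .5 | .05 | 8% | 10% |
| .2 | .4 | .08 | 14% | 19% |
| .2 | .5 | .10 | 19% | 27% |
| .3 | .4 | .12 | 26% | 36% |
| .3 | .5 | .15 | 37% | 52% |

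**Check by simulation.** This used least-squares paths on observed intercepts and slopes, with 2,000 replicates and the skill intercept always in the outcome equation. Without baseline PDA, the b path was significant in 14% (n = 120) and 20% (n = 180) at r1 = .2, r2 = .4, and in 34-37% and 44-51% at r1 = .3, r2 = .5. With baseline PDA added, the rate was 4.0-6.6% in every scenario that had a real a path (a = .26). When baseline PDA was related to the skill intercept but not the slope, there was no inflation (about 5%), because the intercept is already in the model.

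**Indirect effect, true b zero.** These simulations used r1 from .1 to .4 and r2 from .4 to .6.

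- With a = .26 and both paths required to be significant, the unadjusted rate was 7-56% (n = 120) and 10-76% (n = 180), against 4-6% after adjustment.
- With a = 0 and no adjustment, the joint test stayed at or below 4% and the Sobel test at or below 1%.

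**The H2c statistic as written.** (a2·b2)/(se_a2·se_b2) equals z_a × z_b. Its 5% critical value when both paths are null is about 2.18 (simulated; the plan states no cutoff). With a = .26 and b = 0 it exceeded that value in about 40-52% of trials even after adjustment for baseline PDA. Adjustment therefore does not repair this statistic.

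**The case against.** Several points on the other side stand.

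- **The path figure is not available.** The Aim 2 text refers to it and labels paths from it, and C.2.f calls itself a general strategy. The figure could contain a covariate. A reader might infer that the plan certainly omits baseline PDA; the documents support only that the text names none in either place. An unstated adjustment cannot be presumed, because the group's earlier mediation analysis (C.1.b) reports the b path as controlled for treatment condition only.
- **A reader might infer that prior drinking alone could make the indirect effect significant.** It could not under a valid test. The a path is randomised and prior drinking can distort only b, so with no treatment effect on skills a joint or Sobel test stays below its nominal level.
- **The size and sign of the bias are not established.** Section A2 says heavy drinking impairs the processing of new information, and C.1.c reports that higher-IQ participants gained more skill. These make a link to skill slope plausible but do not measure it for baseline PDA. Lighter drinkers might instead start with better skills and gain less, which would bias b against H2b. If the correlation with slope is zero, there is no bias.
- **The skill intercept is already in the model**, so confounding through initial skill level alone is absorbed.

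None of this supplies a safeguard for the link from baseline drinking to skill slope.

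**Conclusion.** The concern holds for H2b on the text as it stands. The b path is not randomised, the text describes no adjustment for baseline drinking, and neither timing nor balance between arms replaces it. Under the assumed correlations the false-positive rate runs from no inflation (5%) to 37% at N = 120 or 52% at N = 180. The lower end is as compatible with the documents as the upper end, and a negative link with skill slope would reverse the direction of bias.

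H2c is affected only through b, and under a valid test only when treatment truly changes skills. The H2c statistic has a separate defect that this point does not resolve.

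The simulation used observed intercepts and slopes in place of the Mplus latent growth model. Baseline PDA is the minimum adjustment: drinking during weeks 0-8, while skills are changing, could also confound the b path.

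**What to change.** In C.2.f and in item 11, state that baseline PDA from the pre-treatment Timeline Follow-Back is a predictor of the skill intercept, the skill slope and follow-up PDA in the models for H2a-H2c, and define the window over which it is computed. If the path figure already includes it, say so in the text.

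An analysis adding PDA from the first month is best left out. If it is wanted, define it as treatment month 1 and label it exploratory. That value is post-randomisation and may itself result from skills already learned, so adjusting for it could remove real mediation.

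The cost is a change of wording: the variable is already scheduled, and no new data or participants are needed. This is a free improvement. The H2c statistic must be corrected separately.
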